### Investigational Protocol: Iowa Cochlear Implant Clinical Research Center Hybrid L24 and Standard Cochlear Implants in Profoundly Deaf Infants

## 1 INVESTIGATIONAL PROTOCOL

The purpose of this feasibility study is to evaluate whether a Nucleus L24 and a FDA approved standard-length device in the contralateral ear can provide useful binaural hearing in pediatric subjects who have bilateral profound hearing loss, meeting the criteria for cochlear implantation. Unlike a conventional cochlear implant, the Nucleus L24 is designed to preserve the regions of the cochlear partition that are apical to the electrode, thus leaving them available for possible future advances in the field of otolaryngology and hearing devices, such as mammalian hair cell regeneration techniques or improved implantable hearing devices. The Nucleus L24 (16 mm) array stimulates the basal turn of the cochlea, in an attempt to preserve the middle and apical regions of the scala media.

Criterion for selection of the Nucleus L24 and a standard-length device group will be parent interest in bilateral implantation and the following criteria: profound bilateral sensorineural hearing loss; lack of benefit from appropriately fit binaural hearing aids worn on a full-time basis; language deficit; and supportive family dynamics. Qualified participants must also meet the following criteria for inclusion and exclusion, respectively.

### 1.1 Criteria for Inclusion:

- 1. Twelve to twenty-four months of age at the time of implantation.
- 2. Audiometric thresholds for frequencies 250 to 8000 Hz in the profound hearing range bilaterally. The type of hearing loss must be categorized as sensorineural in nature.
- 3. English spoken as a primary language (mono-lingual English-speaking family, where English is the primary language).
- 4. Willingness to comply with all study requirements.
- 5. Minimum of three-month hearing aid trial with appropriately fit hearing aids.
- 6. Patent cochlea and normal cochlear anatomy as shown by a CT scan. It is standard clinical practice to perform a CT scan on any patient pursuing cochlear implantation.

### **1.2 Criteria for Exclusion:**

- 1. Medical or psychological conditions that contraindicate undergoing surgery.
- 2. Ossification or any other cochlear anomaly that might prevent complete insertion of the electrode array.
- 3. Developmental disabilities or other conditions that would prevent or restrict participation in the audiological evaluations and clinical trial.
- 4. Hearing loss of neural or central origin.
- 5. Unrealistic expectations on the part of the candidate and/or candidate's family, regarding the possible benefits, risks, and limitations that are inherent to the surgical procedure(s) and prosthetic devices.

- 6. Unwillingness or inability of the candidate to comply with all investigational requirements.
- 7. Active middle ear infection.

# 1.3 Investigational Procedure

## 1.3.1 Design Overview:

The study will be conducted as a repeated-measure, single-subject experiment. A single-subject research design (in which each participant serves as his or her own control) is appropriate because it accommodates the heterogeneity that characterizes hearing-impaired populations. Blinding or masking procedures are not included in the design, as it is not possible to conceal the presence or absence of a cochlear implant from device recipients and/or clinical investigators.

Preoperatively, candidates will be assessed with their current amplification to evaluate their appropriateness for entrance into the study. The candidates' audiometric configuration must meet the above inclusion criteria. That is, the candidate must have a profound sensorineural hearing loss from 250 to 8000 Hz. Prior to testing, the appropriateness of the hearing aid fitting will be assessed and adjustments made if necessary. In cases where amplification has not been used for more than one year, new hearing aids will be fit, worn for a minimum three-month trial and the participants re-evaluated to confirm continuance with the study.

Fifteen infants will receive one Nucleus L24 array and a FDA approved standard-length array on contralateral ears. We will alternate every other subject between the right and left ears as to which ear gets the Nucleus L24. Postoperatively, the right ear only, left ear only, and the bilateral listening modes will be compared with repeated testing through five years of age of the child. These comparisons will help to evaluate the effects of bilateral stimulation using a shorter electrode cochlear implant to possibly preserve the scala media, organ of Corti, and supporting cells for future medical interventions and a standard length implant on the contralateral ear. In addition, we will attempt to compare speech perception and speech/language measure results with age-matched children implanted with standard-length bilateral devices. The following defines the various modes referenced throughout the course of this text:

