## 1.4.5 Audiological Assessment

The degree of hearing loss will be determined by a combination of electrophysiological and behavioral tests including auditory brainstem response testing; otoacoustic emission testing; steady state evoked potential testing; behavioral observation audiometry, visual reinforcement audiometry and/or conditioned play audiometry. Audiological assessment will include unaided and aided audiometric thresholds.

Unaided audiometric thresholds will be obtained for each ear, using insert earphones when possible. Thresholds will also be obtained using conditioned play audiometric (CPA) techniques, visual reinforcement audiometric (VRA) and/or behavioral observation (BOA) techniques for pure-tone air-conduction. The most appropriate testing technique will be used according to the child's age. Bone conduction testing will be completed using the above techniques. Aided audiometric thresholds will be obtained, using narrowband noise, for each ear in the sound-field using standard audiometric techniques, CPA, VRA or BOA with the speakers positioned at 45°-azimuth relative to the participant's head. Results for unaided testing must be reported for the frequencies of 250, 500, 1000, 2000, 4000, 6000, and 8000 Hz. Results for aided testing needs to be reported for the frequencies of 250, 500, 1000, 2000, 4000, 6000, 1000, 2000 and 4000 Hz.

A candidate is only considered enrolled when 1) a properly executed informed consent form has been completed and returned, 2) his/her preoperative candidacy evaluation is accepted, and 3) both forms have been reviewed and approved by the University of Iowa.

Iowa Cochlear Implant Clinical Research Center Hybrid L24 and Standard Cochlear Implants in Profoundly Deaf Infants

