- Phonetically Balanced-Kindergarten (PB-K, Haskins, 1949) in quiet. The PB-K test has multiple 50 word lists. The test will be scored as total number of words correct as well as phonemically. It will be administered in both the unilateral and bilateral listening conditions at 70 dB C.

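### The ear that gets the L24 is set by open alternation, so the next ear is known before a child is accepted and the single-ear comparison is open to selection on ear asymmetry

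*Combined protocol and SAP*

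**What the plan says.** Section 1.3.1 states the sample and the rule together. "Fifteen infants will receive one Nucleus L24 array and a FDA approved standard-length array on contralateral ears", and then "We will alternate every other subject between the right and left ears as to which ear gets the Nucleus L24". It does not say which ear comes first, whether the order is that of consent, enrolment or surgery, or who keeps the sequence. The same section rules out blinding because the presence of an implant cannot be hidden. That reason does not bear on whether the next ear could be withheld until a child is accepted.

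The same section plans the comparison at issue: "the right ear only, left ear only, and the bilateral listening modes will be compared with repeated testing". Section 1.5.3 defines L24-only and standard-only listening conditions. In section 1.5.4.1 the vowel test, the ESP and the PB-K each carry the instruction "It will be administered in both the unilateral and bilateral listening conditions at 70 dB C".

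Information on each ear is collected before acceptance. Section 1.4.5 says "Unaided audiometric thresholds will be obtained for each ear, using insert earphones when possible", and enrolment then depends on the candidacy evaluation being accepted and approved. Section 1.1 requires "Audiometric thresholds for frequencies 250 to 8000 Hz in the profound hearing range bilaterally" and "Patent cochlea and normal cochlear anatomy as shown by a CT scan". Section 1.2 excludes "Ossification or any other cochlear anomaly that might prevent complete insertion of the electrode array". It also contains criteria that need judgement, such as the family's expectations, so acceptance is not mechanical.

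**The concern.** Three things coexist before enrolment: the staff can know which ear is next, they can know how the child's two ears differ, and they have some discretion over acceptance and timing. That is enough for the L24 ear to become related to pre-operative asymmetry, without any intent to bias the study.

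If that happened, part of the L24-versus-standard difference on the vowel test, the ESP and the PB-K would reflect the ear and not the array. These are the tests on which the two arrays are compared within a child. The plan describes no adjustment for baseline ear differences, and 15 children are too few to show afterwards whether a modest imbalance arose by chance or by selection. A paired analysis remains possible, but it would rest on a model assumption that random assignment would have supplied by design.

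**Working it through.** The plan states no power, alpha, SD or effect size for the ear contrast, so it has no figure of its own to reproduce.

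**1. Predictability of the next ear, 15 children**

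- Alternation: 14 of 15 are certain once one assignment is known. With the first ear a coin toss, expected correct guesses are 14.5/15 = 97%.
- Blocks of 4, always guessing the less-used ear: [3 × (0.5 + 2/3 + 2/3 + 1) + 0.5 + 2/3 + 2/3]/15 = 10.33/15 = 69%.
- Blocks of 4 and 6 mixed: about 68% (simulation).
- One permuted list of 8 right and 8 left, first 15 used: about 60% (simulation).
- Simple random list: 50%.

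**2. Bias if unfavoured children are declined**

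Assumptions, none of them from the documents: D is the pre-operative difference between the ear listed for the L24 and the other ear, signed so that positive is the direction the selector favours, with D ~ N(0, s²). A child with D < 0 is declined with probability q. Since the mean of |D| is s√(2/π) = 0.798 s, the mean of D among accepted children is

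0.798 s × [0.5 − 0.5(1 − q)] / [0.5 + 0.5(1 − q)] = 0.798 s × q/(2 − q).

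The first ear is unpredictable, so the average over 15 children is this times 14/15.

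| q | 0.798 × q/(2 − q) | × 14/15 |
|---|---|---|
| 0.10 | 0.798 × 0.10/1.90 = 0.042 s | 0.039 s |
| 0.25 | 0.798 × 0.25/1.75 = 0.114 s | 0.106 s |
| 0.50 | 0.798 × 0.50/1.50 = 0.266 s | 0.248 s |

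If the child is instead swapped with the next candidate, simulation gives about 0.07, 0.16 to 0.17 and 0.30 to 0.31 s. That model needs another candidate to be waiting.

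**3. Outcome scale**

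Let r be the correlation between the asymmetry and the later ear difference in score. The bias in SDs of that difference is r times the last column, and the standard error at n = 15 is 1/√15 = 0.258.

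| q | r = 0.1 | r = 0.3 | r = 0.5 |
|---|---|---|---|
| 0.10 | 0.004 | 0.012 | 0.020 |
| 0.25 | 0.011 | 0.032 | 0.053 |
| 0.50 | 0.025 | 0.074 | 0.124 |

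The extremes are 0.004/0.258 = 0.02 and 0.124/0.258 = 0.48 of a standard error.

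**4. False-positive rate**

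The plan names no test, so a two-sided paired t-test at 0.05 with n = 15 is assumed (20,000 simulated trials, all 15 ears predictable). For r = 0.3 and 0.5 the rejection rate under no array effect is 0.051 and 0.051 at q = 0.10, 0.052 and 0.055 at q = 0.25, and 0.058 and 0.076 at q = 0.50.

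**5. Selection on the child as a whole**

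If acceptance depends only on how promising the child is, with no regard to ear differences, the simulated bias in the ear contrast is 0.000 at q = 0.25 and 0.50.

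**The case against.** The strongest reply is that the exposed contrast is not what the study is judged on. Section 1 asks about useful binaural hearing. Section 1.8 measures success by speech perception and language development, with attempted comparisons against age-matched children. The language tests, the GASP and the MLNT/LNT are all given bilaterally. No L24-versus-standard hypothesis or error rate is stated, and section 1.8 admits limited power. All of this stands and limits the weight of the point. It does not remove it, because section 1.3.1 still says that the single-ear modes will be compared.

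The mechanism is also conjectural. No passage expresses a preference for the better or worse ear, and opposite preferences among staff would offset each other. Bilateral profound loss, normal anatomy, the age window of 12 to 24 months and the three-month hearing-aid trial restrict both the asymmetry and the room to defer a child. Thresholds at this age are imprecise. These points make a large q or r less likely, and at q up to 0.25 and r up to 0.5 the bias is at most 0.053 SD, about a fifth of a standard error. They narrow the opening but do not close it.

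Finally, alternation guarantees a near-equal right/left split at any stopping point. That is a real advantage, but restricted random lists keep nearly all of it.

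**Conclusion.** The concern holds as an avoidable weakness of design, not as evidence of bias. Alternation is stated, no concealment is described, and a single-ear comparison is planned. How far that comparison could be distorted cannot be determined from the documents. Under the assumed ranges (q from 0.10 to 0.50, r from 0.1 to 0.5, selection always in one direction) the effect runs from negligible to about half a standard error. The consequence is for how the single-ear results are interpreted, since the plan sets no error rate for them. Bilateral measures and the age-matched comparisons are not affected. The point is worth considering because the remedy is almost free.

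**What to change.** In section 1.3.1, replace alternation with a computer-generated list, held by someone with no part in candidacy or scheduling. Reveal the ear only once consent and candidacy approval are final. Plan to include side (right/left) in the ear analysis, and report the per-ear baseline thresholds by device. Section 1.4.5 already collects those data, so this part is useful even if allocation has begun.

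Earlier assignments stay visible to staff, so the form of list involves a trade-off (modelled bias at q = 0.10, 0.25, 0.50):

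- **Permuted blocks of 4 and 6, sizes undisclosed:** about 0.015, 0.04 and 0.09 s. The split is 8:7 in about 98% of lists and 9:6 in about 2%. Blocks also hold the balance if recruitment stops early, which matters because section 1.8 says up to 15.
- **One permuted list of 8 right and 8 left, first 15 used:** about 0.01, 0.02 and 0.05 to 0.06 s, always 8:7 if all 15 places are filled.
- **Simple random list:** 0, but the split is 10:5 or worse in 2 × P(Bin(15, 0.5) ≥ 10) = 30% of lists.

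Either restricted list is a sound choice. The cost is one list and two or three sentences, with no extra visits or patients and slightly less certain side balance than alternation. The change does not address unmasked programming or scoring.

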# 1.8 Data Analysis

In order to assess the feasibility of using the Nucleus L24 electrode and the standardlength arrays on contralateral ears, data will be analyzed individually and with group statistics. Because the children implanted in this study will be 12-24 months of age at time of implantation, outcomes as to the success of this study may become clearer as the child ages and their speech and language skills develop. Thus, our primary measure of assessment will change as the child becomes older.

We will measure success of this study by assessing speech perception and speech/language development as described above in the test descriptions (see 1.5.4). We will attempt to compare these results with age-matched children implanted with standard-length bilateral devices on both ears on the same speech perception and speech/language measures. In addition, if possible, we will attempt to compare the same speech perception and speech/language measures on age-matched children implanted with a standard-length device on one ear and a Nucleus S12 implant on the contralateral ear. The independent variable will be whether the child receives Nucleus L24 and standard-length device on one ear and a Nucleus S12 implant on the contralateral ear. The dependent variables will be a set of speech perception and speech/language measures suitable for tracking growth of these traits.

Because this is a feasibility study, we will only be implanting up to 15 infants with Nucleus L24 and standard-length electrode arrays on contralateral ears. We recognize that this small number of subjects may not afford us enough statistical power to adequately answer all questions associated with using these different length electrode arrays in pediatric subjects who have bilateral profound hearing loss. However, it may lend us foundational knowledge to assess whether the device configurations can provide useful bilateral hearing while possibly preserving the scala media, organ of Corti and supporting cells of the ear for future advances in molecular and/or genetic treatments of the inner ear.

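### Must section 1.8 name the within-child contrast by array, given that section 1.3.1 words it by side and section 1.8 describes only comparisons with other children?

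*Combined protocol and SAP*

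**What the plan says.** Section 1.3.1 calls the study a repeated-measure, single-subject experiment in which "each participant serves as his or her own control". On allocation it says: "We will alternate every other subject between the right and left ears as to which ear gets the Nucleus L24". The comparison follows: "Postoperatively, the right ear only, left ear only, and the bilateral listening modes will be compared", with repeated testing up to age five. The next sentence gives the purpose: "These comparisons will help to evaluate the effects of bilateral stimulation using a shorter electrode cochlear implant", with a standard-length implant in the other ear. The section ends by pointing to the mode definitions.

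Section 1.3.2 (Device Description) gives those definitions as the L24 array, the standard-length array and bilateral stimulation. Section 1.5.3 (Listening Conditions) lists L24 only, standard-length only and both together, and presents them as applying to every measure. Section 1.5.4.1 gives the Iowa Children's Vowel Test, the ESP and the PB-K in unilateral and bilateral conditions. Section 1.5.4.2 gives all speech and language tests bilaterally.

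Section 1.8 says "data will be analyzed individually and with group statistics" and that "our primary measure of assessment will change as the child becomes older". It names two comparisons with other, age-matched children, both worded as attempts. It then says "The independent variable will be whether the child receives Nucleus L24 and standard-length device on one ear", and the sentence goes on to place an S12 implant on the other ear. On size it says "we will only be implanting up to 15 infants" and concedes that power may be too low for some questions.

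**The concern.** The own-control design is justified by the heterogeneity of hearing-impaired children, yet the analysis section speaks only of comparisons between children. If the within-child contrast, its visit and its score are not fixed, the headline within-child result could be picked after the data are seen, in a study that is not masked.

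The side wording looks worse still. With the L24 on the right in about half the children and on the left in the rest, a group mean of right minus left nearly cancels the array effect.

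Two smaller points go with this. Section 1.5.3 appears to promise unilateral testing on every measure, while the test entries provide it for only a few. Strict alternation also lets the team know the next L24 side before a candidate is accepted under section 1.4.5, which comes after ear-specific thresholds have been obtained.

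**Working it through.** The documents give no calculation behind the 15 children, so there is no planned figure to reproduce. The checks below use the design as written.

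**1. What the side label would do, and what it does.** Let s = +1 if a child's L24 is on the right and -1 if on the left. Then right minus left = side effect + s × array effect + error, where the array effect is L24 minus standard.

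- Pooled by side, the array effect is weighted by the mean of s. At 15 children alternation gives 8 and 7, so the weight is (8 - 7)/15 = 0.067. At 14, 12 or 10 children it is 0; at 13 it is 1/13 = 0.077; at 11 it is 1/11 = 0.091.
- Labelled by array (multiply each difference by s), the array effect has weight 1 and the *side* effect has weight 1/15 or 0. Alternation is what keeps ear side out of the array contrast.
- Within one child, right versus left is L24 versus standard, so individual results are the same under either label.

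The loss therefore arises only if group data are pooled by side. No section plans that, and section 1.3.1 itself refers to definitions made by array. The data can be labelled by array as long as the implanted side is recorded.

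**2. Which tests carry the single-ear contrast.** Sections 1.5.4.1 and 1.5.4.2 hold 12 entries:

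| Mode stated | Entries | Count |
|---|---|---|
| Unilateral and bilateral | Iowa vowel test, ESP, PB-K | 3 |
| Bilateral only | GASP, MLNT/LNT, six speech/language entries | 8 |
| None stated | IT-MAIS/MAIS (parent questionnaire) | 1 |

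The 11 entries with a stated mode can be run as written, so the broader sentence in section 1.5.3 changes no test. Bilateral-only measures also serve the own-control design: IT-MAIS, speech samples, CDI/MinnCDI and PLS-3 are taken at baseline (section 1.4.6) and again after surgery, which allows change from baseline.

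**3. How much choice is left open.** Visits are at 4, 8, 12, 18 and 24 months, then yearly. This count assumes all are dated from surgery. A child implanted at 12 months reaches the fifth birthday at month 48: 4, 8, 12, 18, 24, 36, 48 = 7 visits. A child implanted at 24 months reaches it at month 36: 6 visits. Reading the limit as the day before the sixth birthday also gives 6 or 7.

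- One score per test: 3 tests × 3 pairwise contrasts × 6 or 7 visits = 54 or 63.
- PB-K is scored by word and by phoneme, ESP has spondee and monosyllable parts, and the vowel test may add babble. With up to 6 scores: 6 × 3 × 6 or 7 = 108 or 126.
- One named visit per test: 3 × 3 = 9 with one score each, and up to 6 × 3 = 18 if the score stays open.

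These are upper counts, because tests are given only when age-appropriate.

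**4. Alternation.** After the first child, 14 of 15 sides are known. A concealed list mixing blocks of 2 and 4 would still be guessed correctly for an expected 10.59 of 15 children (71%), by always guessing the side used less so far. It would allow an imbalance of 2 if accrual stopped mid-block, against 1 under alternation.

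**The case for a change.** The best case for a change is that the within-child comparison is the only one the study can count on, because both comparisons with other children are conditional. Useful binaural hearing is the stated purpose, and showing it within this study needs bilateral against single-ear results in the same child. Section 1.8 refers to the measures but not to this contrast, and a few added words would need no extra children, visits or tests.

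Part of this stands. Section 1.8 fixes no visit, score or method for the within-child comparison, and with unmasked testing a selective summary is possible. It does not follow that the comparison is absent. Section 1.3.1 commits to it in the same combined document, and section 1.8 calls for individual as well as group analysis. The independent-variable sentence is weak evidence of exclusion: it directly follows the comparisons with other children, and its device description is garbled.

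Nor is the usual remedy free. One summary visit per test would make the other visits descriptive, whereas section 1.8 wants measures suited to tracking growth and a primary measure that moves with age. Without a fixed score, up to 18 contrasts would remain.

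**Conclusion.** The concern does not call for a change. The contrast is set out across sections 1.3.1, 1.3.2, 1.5.3 and 1.5.4, and an analyst following all of them would compare L24-only, standard-only and bilateral within the child on the three tests given unilaterally. The side label and the broad sentence in section 1.5.3 are loose wording that changes no result. The 6.7% figure describes an analysis that no section proposes.

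The open choice of visit and score is real, at 54 to 63 possible contrasts with one score per test. It is acceptable in a feasibility study of at most 15 children that states no hypothesis test, admits limited power and sets out to follow development over time. Replacing alternation offers no clear gain: no steering is shown, the size of any bias cannot be computed from the documents, and both ears of every child must be in the profound range.

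This rests on two assumptions: that the implanted side is recorded for each child, and that the results are reported as foundational feasibility findings, as section 1.8 describes them. A confirmatory claim from a single within-child contrast would need that contrast, score and visit fixed beforehand.
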